While promising research is underway to improve engagement/adherence to existing depression EBTs and to develop new treatments, other approaches should be considered. One of these is an existing EBT with a strong research pedigree but has low adoption in clinical care: bright light therapy (BLT), most often administered via a “light box.” BLT was developed out of basic science regarding seasonal affective disorder (SAD). For many years, BLT has been viewed as an appropriate treatment for SAD but not for non-SAD depression. However, recent trials and meta-analyses reveal that BLT yields medium to high clinical benefit for non-SAD depression as well as SAD, as both monotherapy or as an adjunct to ADs. BLT has several advantages over existing pharmacotherapy or psychotherapy. First, at a typical light box purchase price of \$70 to \$110 it is relatively affordable, and many insurance plans reimburse patients for the purchase cost. Second, BLT is hypothesized to work via a different mechanism than pharmacotherapy or psychotherapies, and evidence points to additional benefit when BLT augments other EBTs. Third, properly educated and motivated patients can self-administer BLT at home, alleviating barriers of travel burden and limited access to care—telehealth issues that have been highlighted during the present pandemic. Finally, contraindications are minimal (e.g., skin/eye photosensitivity), side effects are typically minor/transient, and antidepressant action is rapid (within 1-2 weeks). Despite these advantages adoption/promotion of BLT is low, even when patients are not engaged in other depression EBT. This represents a care gap that may be addressed in part with BLT.

Given that BLT has established medium-large efficacy, what is the next step? A large pragmatic effectiveness trial is a logical progression of research: to examine benefit of a deployment-ready BLT approach when delivered to complex real-world patients in an active health care system setting, against a background of other usual care. This trial will evaluate BLT effectiveness with little of the “scaffolding” typical of highly controlled efficacy trials. This R34 pilot will prepare for a future, fully-powered effectiveness trial.

4. Study Design

This is a three-arm randomized controlled trial (RCT), with treatment as usual (TAU; i.e., usual care) underlying all study arms. Following a 2-stage eligibility screening and baseline assessment, patients will be randomly assigned to:

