Adherence promotion (AP) + Motivational Interviewing (MI). This Arm 3 component will focus on monitoring appropriate light box use and guiding participants back to this protocol when there is drift. Ideally, coaches will make an initial check-in phone contact within 72 hours of enrollment, encourage purchase of light box, assist with compensation for light box purchase, and review educational material about the ideal use of BLT. Coaches will make additional AP+MI contacts by phone after 1 week of BLT use. For adherent participants who are using BLT consistent with the ideal protocol, coaches will make one more call in week 3 or 4 to confirm ongoing adherence and to assist participants with the shift to the maintenance phase. For participants who are only partially or weakly adherent, coaches will make up to 6 additional brief contacts to assist, promote use, and help overcome barriers or low motivation to use BLT according to the ideal protocol. In all cases, coaches will employ standardized problem-solving techniques to identify the issue(s), barriers, and facilitators for ideal BLT use, and assist participants in brainstorming possible solutions. Coaches will also monitor for relapse to depression episode, with plan to restart BLT or increase session duration/frequency as needed.

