Demographics data will be collected on all potential participants during the screening process and/or baseline assessment and will include race, ethnicity, sex assigned at birth, gender identity, relationship status, employment status, and education and income information.

Survey Measures

All measures will be administered at the baseline assessment and all follow-up assessments unless otherwise indicated. The surveys will include questions from the following measures, either in part or in their entirety: **Patient Health Questionnaire-9 (PHQ-9); Seasonal Pattern Assessment Questionnaire (SPAQ); Quick Inventory of Depressive Symptomatology, self-report (QIDS-SR); Geriatric Depression Scale (GDS);** the abbreviated **self-report Columbia Suicide Severity Rating Scale (C-SSRS); Altman Self-Rating Mania Scale (ASRM); Generalized Anxiety Disorder-7 (GAD-7); Brief Medication Questionnaire (BMQ); Short Form 6 Dimension (SF-6D); Pittsburgh Sleep Quality Index (PSQI); Reduced Version of the Morningness-Eveningness Questionnaire (rMEQ); Split Week Self-Assessment of Sleep Survey (SASS-Y); Readiness Ruler (RR);**

Non-Standardized Measures to be collected include:

Alternative depression treatments. We will ask participants whether they are currently using, or intend to use, any “alternative” treatments for depression such as BLT (including whether light box purchase was new or had existing), yoga, Tai Chi, mood-enhancing diets (e.g., Mediterranean Diet), exercise, omega-3 fatty acids, St John’s wort, and others.

Satisfaction and Feedback. At the 2-month follow-up assessment, we will ask participants in Arms 2 and 3 about their experience as a participant in this study.

Actigraphy

Following the baseline and 2-month follow-up assessments, participants will be mailed an actigraphy device to wear for 10 days or until the battery dies and then return in supplied postage-paid envelope. We will download/score actigraphy data for sleep and physical activity using ActiLife software, then reset the actigraphy device and reuse it again with additional participants.

Ecological Momentary Assessment (EMA)

Up to 4 days per week during the 9-week acute intervention phase (baseline to 2-month follow-up), and twice weekly thereafter to 6 months, all participants will be sent text and/or email links to a brief EMA REDCap survey about mood and sleep in the last 24 hours. For participants in Arms 2 and 3, the EMA survey will also include brief questions about BLT adherence.

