We will conduct exploratory analyses of the BLT mediation pathway as the extent to which the relation between BLT and outcomes is mediated by changes in participants' 1) sleep (SASS-Y and actigraphy, and PSQI subjective sleep quality), 2) total physical activity, and 3) circadian timing and chronotype. For example, to evaluate the mediating effect of PSQI sleep quality we will regress post-acute treatment PSQI on baseline PSQI and a randomization condition indicator; and we will regress follow-up PHQ-9 at post-acute treatment PSQI and a randomization condition indicator. Using the product coefficients mediation approach, we will use the resulting regression coefficients and standard errors (SEs) to estimate the indirect effect. Because SEs of the products of regression coefficients are not normal, we will use bias-corrected bootstrapping to estimate the SEs for the indirect effect. We will use a similar approach for the MI pathway to test the mediating effect of participants' increased readiness to change on BLT adherence.

Analysis of secondary outcomes. Continuous measures over time will be modeled with HLM methods described above. Health service use can be categorized into binary (e.g., met threshold for medication possession ratio, had > 1 hospitalization) and count outcomes (e.g., N of ED visits, primary care visits). Binary outcomes will be modeled with multivariable logistic regression, and the coefficient of study arm membership (e.g, 0=TAU, 1=TAU+BLT+AP & TAU+BLT) is the coefficient of primary interest. Count outcomes are modeled with either multivariable Poisson or negative binomial regression depending on which yields optional fit.

BLT process outcomes. To examine the effects of adherence and MI elements, we will contrast Arms 2 vs. 3 across months 2, 4, and 6, comparing: (a) % cumulative light box purchase; (b) % cumulative compensation for light box purchase; and (c) mean EMA-adherence (aka, dose). We will conduct these analyses using methods similar to those for secondary outcomes; however, the analysis sample will be restricted to Arms 2 and 3. We will describe similar metrics in the TAU condition (Arm 1).

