# BACKGROUND

## Rationale and research questions

BLT Pilot aims to test the feasibility of conducting a controlled clinical trial designed to evaluate the effectiveness and cost-effectiveness of minimal and enhanced “encouragement” to initiation and regular use BLT for treatment of an incident unipolar depressive episode among adult members of the KPNW medical plan. Encouragement includes motivational interviewing, education, and tools for using BLT with high adherence.

Our primary clinical outcome is the PHQ-9 at post-acute treatment (2 months follow-up). Our primary process outcomes are initiation of BLT therapy and adherence to best BLT practices.

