## Moderation and mediation

In addition to primary outcome analyses we will conduct exploratory analyses of moderation using variables identified through previous research and clinical expertise, specifically indication of pharmacotherapy use (1=yes, 0=no), age (continuous), gender (1=female, 0=male), race and ethnicity (1=racial/ethnic minority, 0=non-Hispanic white), baseline PHQ-9 (1=clinically elevated, 0=below clinical range), and EHR indication of mental health comorbidities such as eating disorders, anxiety (1=comorbidity, 0=no comorbidity). Moderation will be indicated by a significant time x arm x moderator interaction in HLM.

We propose to conduct exploratory analyses of the BLT mediation pathway as the extent to which the relation between BLT and outcomes is mediated by changes in participants' 1) sleep (sleep diary and actigraphy, and ISI subjective sleep quality), 2) total physical activity, and 3) circadian timing and chronotype. For example, to evaluate the mediating effect of ISI sleep quality we will regress post-acute treatment ISI on baseline ISI and a randomization condition indicator; and we will regress follow-up PHQ-9 at post-acute treatment ISI and a randomization condition indicator. Using the product coefficients mediation approach, we will use the resulting regression coefficients and standard errors (SEs) to estimate the indirect effect[10-12]. Because SEs of the products of regression coefficients are not normal, we will use bias-corrected bootstrapping to estimate the SEs for the indirect effect.[12] We will use a similar approach for the MI pathway to test the mediating effect of participants' increased readiness to change on BLT adherence.

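### Actigraphy is mailed after the baseline and 2-month assessments, so its baseline can be partly post-randomisation and its follow-up cannot precede the 2-month PHQ-9

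*Protocol*

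**What the plan says.** The device schedule is in the protocol, Section 6, Actigraphy: "Following the baseline and 2-month follow-up assessments, participants will be mailed an actigraphy device to wear for 10 days or until the battery dies". The recordings are scored for sleep and physical activity.

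On randomisation, Section 4 says: "Following a 2-stage eligibility screening and baseline assessment, patients will be randomly assigned to" one of the three arms. Neither that section nor the Randomization paragraph of Section 6 mentions baseline wear. In Arm 3, Section 6 says that, ideally, "coaches will make an initial check-in phone contact within 72 hours of enrollment". No timing is given for the two Arm 2 messages. The EMA paragraph starts the acute phase at baseline: surveys are sent "during the 9-week acute intervention phase (baseline to 2-month follow-up").

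Actigraphy has a defined analytic role. The protocol's mediation text lists "sleep (SASS-Y and actigraphy, and PSQI subjective sleep quality), 2) total physical activity" among the mediators. The SAP (Moderation and mediation) lists "sleep (sleep diary and actigraphy, and ISI subjective sleep quality), 2) total physical activity". The questionnaires differ between the two documents, but actigraphy has the same place in both. In the worked example, the post-acute mediator is regressed on its baseline value and arm, and a follow-up PHQ-9 is then regressed on the post-acute mediator and arm. The month of that PHQ-9 is not given. Protocol Section 2 and SAP Aim 2 also compare pre-post change in the proposed mediators for every arm contrast.

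The SAP (Rationale and research questions) fixes the main time point: "Our primary clinical outcome is the PHQ-9 at post-acute treatment (2 months follow-up"). Both SAP hypotheses refer to the same time point.

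**The concern.** Two features of the timing conflict with the planned use.

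First, a baseline covariate or pre value should be fixed before randomisation. Here both randomisation and mailing follow the baseline assessment, and the text does not order them. If wear falls after assignment, the value can already carry some effect of encouragement or light in Arms 2 and 3 but not in Arm 1. Subtracting it, or adjusting for it, then removes part of the arm-to-mediator effect being estimated.

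Second, a mediator must be measured before the outcome it is said to explain. Wear that starts after the 2-month assessment cannot show that a change in sleep or activity came before the PHQ-9 score recorded at that assessment.

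At stake are the actigraphy mediation estimates and the pre-post contrasts on actigraphy sleep and total physical activity. Activity is the more exposed of the two, because the protocol's list of survey measures contains no physical-activity scale.

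**Working it through.** The plan states no figure on this point, so the check is a day count.

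**Inputs from the documents**
- Wear lasts 10 days, or less if the battery fails (protocol, Actigraphy).
- The first Arm 3 contact is ideally by day 3, from 72 hours (protocol, Adherence promotion).
- Antidepressant effect is expected early: "antidepressant action is rapid (within 1-2 weeks") (protocol Section 3).
- Assessments are at months 2, 4 and 6.

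**Assumptions, because the documents are silent**
- Day 0 is the baseline assessment, and randomisation follows without delay.
- The device arrives d = 1 to 7 days after mailing.
- First light-box use is on day s = 3 to 21.
- Two months is about 61 days.

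**Baseline wear.** Wear runs from day d to day d + 9. The number of wear days on or after day s is min(10, max(0, d + 10 − s)).

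| Delivery d | Wear days | s = 3 | s = 7 | s = 10 | s = 14 | s = 21 |
|---|---|---|---|---|---|---|
| 1 | 1–10 | 8 | 4 | 1 | 0 | 0 |
| 3 | 3–12 | 10 | 6 | 3 | 0 | 0 |
| 5 | 5–14 | 10 | 8 | 5 | 1 | 0 |
| 7 | 7–16 | 10 | 10 | 7 | 3 | 0 |

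The s = 3 column also counts wear days on or after a day-3 coach contact: 8 to 10 of 10. Overlap with light exposure itself runs from 0 to 10 days, depending on when the box is bought and first used.

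**Effect on the estimates.** Let δ be the true arm effect on the mediator, f the fraction of δ already present in the baseline wear of the active arm, and b the slope of the follow-up mediator on its baseline.
- Change score: the contrast is δ − fδ = δ(1 − f).
- Baseline-adjusted model: the recorded baseline is B = B₀ + fδ·arm. Substituting B₀ = B − fδ·arm into b·B₀ + δ·arm gives an arm coefficient of δ(1 − bf).

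With b between 0 and 1, both shrink towards zero, the change score by more. Neither f nor b can be obtained from the documents.

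**Follow-up wear.** It runs from d to d + 9 days after the 2-month assessment, that is from days 1–10 to days 7–16. Wear days before the 2-month PHQ-9: 0 for every d. Gap from the end of wear to the month-4 PHQ-9: 61 − (d + 9), which is 51 days for d = 1 and 45 days for d = 7. Time order therefore fails for month 2 and holds for months 4 and 6.

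**The case against.** **The mediation model may not use the 2-month PHQ-9.** The protocol's Assessments paragraph separates the post-acute assessment at 2 months from follow-up assessments at months 4 and 6. If follow-up PHQ-9 in the mediation text means the later ones, mediator precedes outcome. This stands as a possible reading. It is not settled, because the Actigraphy paragraph and the SAP's statement of the primary outcome also call month 2 a follow-up. A reader might infer that the plan certainly reverses mediator and outcome. The documents do not show that; they show that the order fails for the primary time point and that the month is left open.

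**Contamination of the baseline is possible, not demonstrated.** The 72-hour call is an ideal and applies to Arm 3 only. The interval from baseline to the randomisation call is not stated. A light box must still be bought and received. The early onset that the protocol cites concerns antidepressant action, not actigraphic sleep or activity. All of this stands. A reader might infer that a set percentage of the mediator effect is lost; the documents give no basis for any such figure.

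**The analyses are exploratory and have substitutes.** The protocol says the pilot is not powered for mediation. PSQI, SASS-Y and rMEQ are collected at the assessments themselves, and EMA records sleep before month 2. This limits the importance of the point but does not remove it. The protocol also says the mediation analyses are run as a rehearsal of the confirmatory trial's methods, and measurement timing is part of what is rehearsed. The substitutes cover sleep and chronotype, not total activity.

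**Holding back the intervention is not a free remedy.** A reader might infer that randomisation or active-arm contact should wait for wear to end. That would age the baseline PHQ-9, risk loss before randomisation and cut across the protocol's own contact target. The point does not need it.

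**Conclusion.** The point holds as a limited defect of timing and specification. As written, nothing prevents the actigraphy baseline from being partly post-randomisation in Arms 2 and 3. With prompt randomisation and delivery in 1 to 7 days, 8 to 10 of the 10 wear days fall on or after a day-3 coach contact, while the number under light-box use could be anything from 0 to 10. The size of any resulting bias is unknown; if the early effect has the same direction as the later one, the bias is towards no effect.

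The follow-up part rests on the text alone: none of the second wear precedes the 2-month PHQ-9. Actigraphy sleep and physical activity therefore cannot be time-ordered mediators of the SAP's primary outcome. They can be for months 4 and 6, if the plan says that those are the outcomes used.

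The primary PHQ-9 comparison and the questionnaire mediators are unaffected.

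**What to change.** 1. **Mail the second device about two weeks before the 2-month assessment**, so that wear ends by the PHQ-9 date. Mailed 14 days ahead, the last wear day is d − 5 relative to the assessment: 4 days before it for d = 1, the day itself for d = 5, 2 days after for d = 7. Where delivery is slow, leave out wear days after the PHQ-9 date.
2. **For second wear already done after the 2-month assessment**, relate actigraphy only to PHQ-9 at months 4 and 6. In both documents, name the PHQ-9 month paired with each mediator.
3. **Record wear dates against randomisation**, and use only pre-randomisation wear days as the actigraphy baseline. State in the protocol how mailing, wear and randomisation are ordered in practice.
4. **Where a participant has no such days**, compare 2-month actigraphy between arms without that baseline; randomisation protects this comparison. For sleep, baseline PSQI or SASS-Y can serve as the covariate.

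The cost is an earlier mailing date, a few lines of text and the logging of wear dates. Some precision is lost where no clean actigraphy baseline exists, and for those participants the pre-post actigraphy contrast becomes a post-only comparison. Randomisation and intervention contact stay as planned. With completion estimated for May 2024, much of the wear may already be done, so items 2 to 4 may matter most.

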- Arm 1: Treatment as Usual (TAU) control: A “usual care” control group (e.g., antidepressants, watchful waiting, psychosocial therapy, or no treatment, all determined by the participant in consultation with their TAU providers). All TAU will be recorded for all participants in all study conditions; or
- Arm 2: TAU + Minimal BLT Encouragement: TAU plus two minimal communications (mailed letter, secure EHR message, email, or text) identifying BLT as a promising treatment and outlining steps for participants to self-initiate. Arm 2 will not include any phone coaching or adherence promotion.
- Arm 3: TAU + Enhanced BLT Encouragement + Adherence Promotion + MI: TAU plus 2-6 brief calls to encourage BLT use, advise on purchase of a light box (LB) that meets all ideal technical

standards, assist with obtaining compensation for LB purchase, educate for correct LB use, and provide motivational interviewing (MI) as needed to promote adherence.

Outcomes will be assessed at baseline, 2, 4, and 6 months. The acute intervention period will be for 2 months. The primary outcome will be scores on the Patient Health Questionnaire-9 (PHQ-9), selected as representative of how depression is assessed in many usual care settings, consistent with effectiveness research principles.

5. Study Population

a. Number of Subjects

We will enroll 90 to 100 participants.

b. Inclusion and Exclusion Criteria

Potentially eligible individuals will be screened at two points in the recruitment phase: 1) preliminary identification of likely participants via a search of KPNW electronic health record (EHR) and 2) phone or online screening survey.

EHR inclusion criteria:

- Age 18-69 years, inclusive, and
- New episode of unipolar depression within the last month, defined as: New ICD-10 diagnosis of SAD or unipolar depression (i.e., major depression, minor depression, depression not otherwise specified, and/or adjustment disorder with depressed mood) AND usual care administration of the PHQ-9 depression scale in the last 30 days, with a total score of 10 or higher, and
- Participant must have a kp.org MyChart account, with evidence of use in the last 12 months.

EHR exclusion criteria:

- Chronic depression: ICD-10 diagnosis of SAD or unipolar depression in the 6 months prior to case-identification;
- Elevated PHQ-9 (score of 10 or higher) in the 6 months prior to case identification.

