- Active EHR diagnoses and prescriptions representing any of the following contraindications for BLT: Conditions that might render skin or eyes more vulnerable to phototoxicity (e.g., ophthalmic disorders such as cataract, macular degeneration, glaucoma, retinitis pigmentosa; disorders affecting the retina such as retinopathy, diabetes, herpes); or photosensitive skin; or if they are taking a photosensitizing medication or herb (e.g., St. John's wort or a psoralen).
- EHR-recorded diagnoses of bipolar disorder I or II.

Screening inclusion criteria:

- Elevated PHQ-9 (score of 10 or higher);
- Able and willing to conduct study assessments and phone coaching in English;
- Phone and internet access.

Screening exclusion criteria:

- Participation barriers (e.g., terminal end-stage cancer, moving out of the region, no locator information);

- Contraindicated diagnoses or medications (see EHR exclusion criteria above) in case these are known to patients but are not EHR-recorded (e.g., if they were diagnosed with a contraindicated condition before becoming a KP member and have not yet sought care for it);
- Contraindicated diagnoses or medications (see EHR exclusion criteria) newly reported that were not captured in the EHR;
- Emergent bipolar, manic, mixed symptoms that may not have been formally diagnosed yet (e.g., significant mood swings, excessive increases in energy, dramatically less need for sleep).

In the event of a screen failure, or when a potential participant is contacted but declines participation, minimal demographic data collected (such as age, sex, race, ethnicity), and reason for declining will be retained for review. This data may help inform future study design.

c. Vulnerable Populations

Vulnerable Populations (VPs)	Include/Exclude	Rationale
Pregnant women	Include	Pregnancy has no known vulnerabilities for BLT. Further, BLT may be a valuable alternative treatment for pregnant women who might be hesitant to take antidepressants.
Children	Exclude	N/A
Neonates of uncertain viability or nonviable neonates	Exclude	N/A
Prisoners	Exclude	N/A

d. Setting

This study will be conducted by study staff at Center for Health Research (CHR), among the KPNW adult membership. Participants will be able to conduct all study activities from home.

e. Recruitment Methods

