EHR Identification of Potential Recruitment Pool. We will run an EHR case-finding program as needed for the projected 16-month recruitment period to generate an initial outreach list of potentially eligible individuals. After each recruitment list is generated, we will send a secure EHR message to each individual's primary care provider (PCP) and mental health specialist (e.g., psychiatrist) if applicable. In this message, we will state our intent to reach out to the patient unless we hear from the provider within three business days that it would be unwarranted (e.g., due to more acute condition for which other health care should be primary).

Once an individual has been identified once by this EHR search program, they will be excluded from subsequent runs of the program to avoid multiple waves of contact.

Recruitment Mailing, Emailing, Online Screening, and Calls. For patients not opted out by clinician(s), we will mail/email a recruitment packet containing the recruitment letter, recruitment flyer, and a copy of the consent information sheet. Interested patients have the option to complete the screening survey online. For those who screen eligible online, study staff will follow up by phone to obtain verbal informed consent as described in Section F. Patients also have the option to opt out online.

If the screening survey is not completed online, study assessment staff will begin making recruitment calls to those who have not preemptively declined at least two calendar days after the recruitment packet is sent. If a potential participant did not receive the recruitment packet, upon request, we will email the recruitment packet to the individual. The consent and the recruitment flyer will also be available as downloadable PDF documents on the public access study recruitment website (no account needed). We will use IRB-approved email templates and will follow CHR guidelines in emails sent to potential participants regarding this study.

During the recruitment call, study staff will explain the study and answer questions. For those individuals who are interested, study staff will complete the screening survey. Individuals who pass the screening survey will be invited to complete the baseline survey after study staff obtains verbal informed consent as described in Section F.

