Analysis of primary outcome. For our PHQ-9 primary outcome, we will test whether there are differences in score trajectories across time between arms with two-level hierarchical linear models (HLMs) in a growth curve framework. The first level of the model will include time as a predictor, modeling within-person variation. The second level will include a dummy variable for arm (e.g., 1=TAU+BLT+AP or TAU+BLT, 0=TAU) as the predictor variable for both the random effects of the intercept and slope for time. A significant coefficient for arm on the time slope would indicate that there are different trajectories across time for BLT arms versus TAU.

We will probe any significant arm x time interactions by graphing the simple-effects equations to determine whether the observed pattern is consistent with hypotheses.

Moderation and mediation. In addition to primary outcome analyses we will conduct exploratory analyses of moderation using variables identified through previous research and clinical expertise, specifically indication of pharmacotherapy use (1=yes, 0=no), age (continuous), gender (1=female, 0=male), race and ethnicity (1=racial/ethnic minority, 0=non-Hispanic white), baseline PHQ-9 (1=clinically elevated, 0=below clinical range), and EHR indication of mental health comorbidities such as eating disorders, anxiety (1=comorbidity, 0=no comorbidity). Moderation will be indicated by a significant time x arm x moderator interaction in HLM.

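### The baseline PHQ-9 moderator is split at an unstated cut-off that, on the protocol's only definition, everyone had to clear to enter, so one group may be tiny or empty

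*Protocol*

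**What the plan says.** The Protocol (6.a Data Analysis, Moderation and mediation) and the SAP (Moderation and mediation) list the same moderators. Age is continuous. Baseline severity is binary: "baseline PHQ-9 (1=clinically elevated, 0=below clinical range". Neither document attaches a number to this split. The criterion is: "Moderation will be indicated by a significant time x arm x moderator interaction in HLM".

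The entry rules are in Protocol 5.b. The EHR criteria require a usual-care PHQ-9 in the last 30 days "with a total score of 10 or higher". The screening criteria require it again: "Elevated PHQ-9 (score of 10 or higher"). The EHR exclusions use the same number for earlier episodes: "Elevated PHQ-9 (score of 10 or higher) in the 6 months prior to case identification". The documents define an elevated score nowhere else.

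Baseline is a later and separate step. Protocol 5.e says "Individuals who pass the screening survey will be invited to complete the baseline survey after study staff obtains verbal informed consent", and Protocol 6 (Survey Measures) says "All measures will be administered at the baseline assessment and all follow-up assessments unless otherwise indicated". No PHQ-9 threshold is re-applied at baseline. The baseline score is also the first outcome value: "Outcomes will be assessed at baseline, 2, 4, and 6 months" (Protocol 4).

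**The concern.** The moderator divides the sample at or near the line that every participant had to clear twice to get in. If elevated means 10 or higher, nobody is in group 0 by design. People reach it only by scoring lower at baseline than at screening, through measurement noise or early improvement. A comparison of severe with milder depression therefore becomes a comparison of most of the sample with those who happened to drop under the threshold.

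Whether benefit depends on baseline severity is one of the questions this pilot rehearses for the full trial. A sparse group 0 makes the three-way term imprecise, and an arm with nobody coded 0 makes it impossible to estimate for contrasts involving that arm. If the coding were carried into the full trial with the same entry rule, the low share coded 0 and the loss of information would go with it. The primary PHQ-9 analysis is not at stake.

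**Working it through.** **Possible readings of the cut-off**

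- Cut-off 10, separate baseline survey score (the natural reading of Protocol 5.e and 6): group 0 is only those who fell below 10 after screening.
- Cut-off 10, screening score used as baseline: the moderator is constant and the term does not exist. Nothing in the documents suggests this is intended.
- Cut-off below 10: group 0 is smaller still.
- Cut-off above 10: group 0 fills, but calling it below the clinical range conflicts with 5.b, and the number is still missing.

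**Inputs**

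From the documents: 90 participants, allocated 1:1:1, so about 30 per arm; two entry gates at 10 or higher. The plan gives no figure for the size of group 0, so there is none to reproduce.

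Assumed, because the documents give no PHQ-9 distribution or screening-to-baseline change: normal scores rounded to 0–27, with mean 8–14 and SD 4.5–5.5 before the gates are applied; correlation 0.70–0.95 between any two of the EHR, screening and baseline scores; average fall between screening and baseline of 0, 1, 2 or 3 points.

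**Formulas**, with p the share coded 0 and q = 1 − p:

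- Interaction standard error relative to an even split: √(0.25 / (p·q)).
- Chance that one side of pooled Arms 2+3 vs Arm 1 has nobody coded 0: 1 − (1 − q³⁰)(1 − q⁶⁰).
- The same for a two-arm contrast: 1 − (1 − q³⁰)².
- For at least one of the three arms: 1 − (1 − q³⁰)³.
- Linear information kept: squared correlation of the 0/1 code with the baseline score.

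**Share coded 0, no average fall**

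| Mean, SD | r = 0.70 | r = 0.85 | r = 0.95 |
|---|---|---|---|
| 8, 4.5 | 21.6% | 13.6% | 7.2% |
| 10, 5.5 | 15.8% | 10.0% | 5.3% |
| 12, 4.5 | 10.4% | 6.6% | 3.4% |
| 14, 4.5 | 6.3% | 4.0% | 2.1% |

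At p = 21.6%, √(0.25 / (0.216 × 0.784)) = 1.22. At p = 2.1%, √(0.25 / (0.021 × 0.979)) is about 3.5. Also at 2.1%, q³⁰ is about 0.53 and q⁶⁰ about 0.28. The empty-side chance is then about 66% (pooled), 78% (two arms) and 90% (any of three arms). At 21.6% each of these is 0.2% or less.

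**Ranges over all settings**

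| Average fall | Coded 0 | Of 90 | SE ratio | Information kept | Empty side, pooled |
|---|---|---|---|---|---|
| 0 | 2%–22% | 2–19 | 1.2–3.5 | 8%–49% | 0%–66% |
| 1 | 6%–31% | 6–28 | 1.1–2.1 | 18%–57% | 0%–17% |
| 2 | 12%–43% | 11–38 | 1.0–1.5 | 29%–62% | 0%–2% |
| 3 | 20%–54% | 18–49 | 1.0–1.2 | 40%–64% | about 0.1% or less |

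**Cross-checks.** A simpler model with only the screening gate (mean 11–15, SD 5, same correlations, no fall) puts 3% to 20% below 10 at baseline, about 3 to 18 of 90. Generalised least squares in a two-level growth model with visits at 0, 2, 4 and 6 months and 30 vs 60 participants gave median SE ratios of 1.23 (mean 8, SD 4.5, r 0.70) and 2.00 (mean 12, SD 5, r 0.85), in line with the formula. At mean 14, SD 4.5, r 0.95, 62% to 67% of simulated trials had an empty side.

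**The case against.** The size of the problem comes from assumptions, not from the documents. The range runs from no practical difficulty to a term that usually cannot be estimated. With no average fall, the pooled empty-side chance is below 5% in 15 of 36 settings, with a median of about 12%. A 2- or 3-point fall before baseline nearly removes the risk of an empty group, and the documents favour no value of the fall over another. This stands, and it is why the claim is only that group 0 may be small or empty.

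The interaction would be imprecise under any binary coding. In raw SD units for Arms 2+3 vs Arm 1 with N = 90, the effect detectable with 80% power is 2.80 × √(1/(60s) + 1/(30s) + 1/(60(1−s)) + 1/(30(1−s))), where s is the share coded 0. An even split gives 2.80 × √0.20 = 1.25 SD, and s = 10% gives 2.80 × √0.556 = 2.1 SD. Neither is a realistic target. This too stands: the coding worsens an estimate that was already weak.

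The Preliminary data evaluation section of both documents promises a check of distributions before analysis, so a sparse group would be noticed. But neither document names a replacement, so any new cut-off would be chosen after seeing the data.

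A threshold question can be legitimate, and the information figures presume linear moderation. That is fair, but a threshold analysis needs a stated threshold, and this one has none.

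**Conclusion.** The concern holds and is minor. The documents alone establish that the cut-off is missing and that, on their only definition of elevated, group 0 is limited to people whose score fell below 10 after screening. How many that is depends on the assumed score distribution, retest correlation and change before baseline: 2% to 22% with no average fall, and 20% to 54% with a 3-point fall. The loss of information does not depend on choosing among these assumptions, since the 0/1 code keeps at most about 64% of the linear information in every setting tried, and as little as 8%. The consequence is confined to one exploratory moderator in a pilot that both documents describe as too small for an adequately powered or confirmatory test.

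**What to change.** In both Moderation and mediation sections, enter PHQ-9 severity as a centred continuous moderator, as is already done for age. Because the month-0 PHQ-9 is also an outcome in the growth model, state how it is handled in this one model. Two options work:

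- **Option 1.** Model months 2, 4 and 6, with baseline PHQ-9 as covariate and moderator. The time × arm × moderator term then covers only change after month 2, so the arm × baseline term at month 2 must also be named as evidence of moderation.
- **Option 2.** Keep all four visits and the stated criterion, and use the continuous screening PHQ-9 as the moderator. It is slightly noisier. Under the no-fall assumptions it keeps 82% to 100% of the baseline score's squared correlation with underlying severity, against 6% to 43% for the 0/1 code (14% to 52% with a 1-point fall, 25% to 59% with a 2-point fall).

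Any binary version kept for description should have a stated cut-off that splits the enrolled range.

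The cost is a few lines in each document. Both scores are already collected, and the primary analysis does not change.
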